#### **10.4 CRITERIA FOR SUBJECT SELECTION (IN- AND EXCLUSION)**

Following receipt of verbal and written information about the clinical trial, the subject must provide **signed and dated informed consent** before any trial related activity is carried out.

Any implementation of national requirements/law for the subject's participation in the clinical trial will be ensured and will be described in submission documentation to authorities/ethics committees, as applicable.

##### **10.4.1 Inclusion Criteria**

1. Following verbal and written information about the trial, subject must provide informed consent documented by signing the Informed Consent Form (ICF) prior to any trial-related procedures
2. Subjects with 5 to 9 clinically typical, visible and discrete AKs within a contiguous 25 cm^2 treatment area on the face or scalp. Actinic keratosis should be confirmed by histopathology of one of the AKs prior to randomisation.
3. Subject at least 18 years of age
4. Female subjects must be of either:
  - a. Non-childbearing potential, i.e. post-menopausal or have a confirmed clinical history of sterility (e.g. the subject is without a uterus) or,
  - b. Childbearing potential, provided there is a confirmed negative urine pregnancy test prior to trial treatment, to rule out pregnancy.
5. Female subjects of childbearing potential must be willing to use highly effective methods of contraception (Pearl index < 1%) at study entry until Week 20. These methods of contraception are defined as:
  - abstinence (when this is in line with the preferred and usual lifestyle of the subject)
  - vasectomised partner (partner should be the sole partner for the subject)
  - an intrauterine device
  - double barrier method defined as two distinct methods (either two actual barrier methods or one actual barrier method and one hormonal method)

---

 Female subjects are considered of childbearing potential unless they have been hysterectomised or have undergone tubal ligation or have been post-menopausal for at least one year prior to first visit..

- hormonal contraceptive (oral hormonal birth control, oestrogenic vaginal ring, percutaneous contraceptive patches, implants and injectables) for at least one menstrual cycle prior to enrolment.

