### 3.1 SCHEDULE/CHART OF TRIAL PROCEDURES

#### 3.1.1 Screening and Treatment Period

Visit Number	Screening	Treatment Period								
	1	2	3	4	5	6	7 	8 	9 	10 
Day/Week (window)	(-42 to -14 days)	Day 1	Day 4 (+2 days)	Week 2 Day 15 (±2 days)	Week 4 Day 29 (±3 days)	Week 8 Day 57 (±3 days)	3 days after Visit 6 (+2 days)	Week 10 14 days after Visit 6 (±2 days)	Week 12 28 days after Visit 6 (±3 days)	Week 16 56 days after Visit 6 (±3 days)
Informed consent	X 									
In-/exclusion criteria	X	X 								
Medical/surgical History	X									
Concurrent diagnosis	X	X 								
AK and SCC treatment history	X									
Concomitant medications, treatments, procedures	X	X	X	X	X	X	X	X	X	X
Brief physical exam 	X	X				X				X
Vital signs	X									
Demographics	X									
Height and weight	X									
Fitzpatrick skin type	X									
Urine pregnancy test 	X					X				X
Identify selected treatment area	X									
Mark selected treatment area on skin		X				X 				
Biopsy of one AK lesion	X									
Biopsy if suspicion of SCC etc.			X	X	X	X	X	X	X	X
Randomisation		X								
AK count	X	X				X				X

Visit Number	Screening	Treatment Period								
	1	2	3	4	5	6	7 	8 	9 	10 
Day/Week (window)	(-42 to -14 days)	Day 1	Day 4 (+2 days)	Week 2 Day 15 (±2 days)	Week 4 Day 29 (±3 days)	Week 8 Day 57 (±3 days)	3 days after Visit 6 (+2 days)	Week 10 14 days after Visit 6 (±2 days)	Week 12 28 days after Visit 6 (±3 days)	Week 16 56 days after Visit 6 (±3 days)
Dispense medication		X				X 				
Return medication			X 		X 		X 		X 	
Compliance			X	X 	X 		X	X 	X 	
Field assessment for SCC, BCC or neoplasia			X	X	X	X	X	X	X	X
Local skin response (LSR)		X	X	X	X	X	X	X	X	X
Adverse events		X	X	X	X	X	X	X	X	X

1. Only for subjects who are not completely cleared in the selected treatment area at Week 8. Subjects who have cleared should proceed to the Follow –up period at Visit 11
2. Can be performed prior to Visit 1
3. To be checked at Visit 2
4. Including general appearance, regional lymph nodes and dermatologic examination of the skin in general
5. Females of childbearing potential only
6. Imiquimod only
7. Ingenol mebutate only

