### **10.1.3 Individual Visits**

#### Screening (Visit 1, -42 to -14 days)

Eligibility will be checked according to the inclusion and exclusion criteria and the subject will sign the study-specific consent form in the presence of the investigator or his/her designee prior to any screening procedures taking place.

The following information will be recorded:

- Date of birth, sex, race, ethnic origin (self-report), height, weight, Fitzpatrick skin type, relevant medical/surgical history, concurrent diagnoses, concomitant medication, AK and SCC treatment history.
- Abbreviated physical examination including general appearance, regional lymph nodes and dermatologic examination of the skin in general.
- Vital signs (resting blood pressure and heart rate) and oral or ear temperature.

The selected treatment area will be identified by the dermatologist and documented on the study transparency using a three-point landmark technique. Detailed instructions for the three-point landmark technique are given in [Appendix IV](#).

A biopsy will be taken of one AK lesion in the selected treatment area (see [10.7.4](#)) for histological confirmation of AK.

Female subjects of childbearing potential will have a urine pregnancy test.

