#### Visit 2 (Day 1)

Subject eligibility will be checked according to the inclusion and exclusion criteria. Once eligibility is confirmed, assessment of the selected treatment area, including LSRs and AK lesion count will be performed.

---

The subjects will be randomised to treatment with either ingenol mebutate gel or imiquimod cream. A trial medication kit will be assigned through an Interactive Web Response (IWR) System. The selected treatment area will be marked on the skin and the first dose of study medication will be applied under the supervision and management of the trial personnel (the subsequent doses will be applied at home).

Visit 3 (Preferred on Day 4, with a visit window of +2 days)

Visit 3 will include:

- Clinical assessment of neoplasia in the selected treatment area (biopsy if there is suspicion of SCC, BCC or other neoplasia)
- Dermatologic examination of the selected treatment area(s) including LSRs
- Reporting of (S)AEs (see [Table 2](#))
- Reporting of concomitant medication, treatments and procedures
- Return of trial medication (only for subjects treated with ingenol mebutate)
- Trial medication compliance

Visit 4 (Week 2, Day 15 ± 2 days)

Visit 4 will include:

- Clinical assessment of neoplasia in the selected treatment area (biopsy if there is suspicion of SCC, BCC or other neoplasia)
- Dermatologic examination of treated selected treatment area(s) including LSRs
- Reporting of (S)AEs (see [Table 2](#))
- Reporting of concomitant medication, treatments and procedures
- Trial medication compliance (for subjects treated with imiquimod)

Visit 5 (Week 4, Day 29 ± 3 days)

Visit 5 will include:

- Clinical assessment of neoplasia in the selected treatment area (biopsy if there is suspicion of SCC, BCC or other neoplasia)
- Dermatologic examination of the selected treatment area(s) including LSRs
- Reporting of (S)AEs (see [Table 2](#))
- Reporting of concomitant medication, treatments and procedures
- Return of trial medication and trial medication compliance (for subjects treated with imiquimod)

---

Visit 6 (Week 8, Day 57 ± 3 days)

Visit 6 will include:

- Clinical assessment of neoplasia in the selected treatment area (biopsy if there is suspicion of SCC, BCC or other neoplasia)
- Dermatologic examination of the selected treatment area including LSRs and AK count.
- Reporting of (S)AEs (see [Table 2](#))
- Reporting of concomitant medication, treatments and procedures

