- Urine pregnancy test for female subjects of childbearing potential
- An abbreviated physical examination

Subjects who are not completely cleared in the selected treatment area will be retreated with a Second Treatment Cycle (Visits 7 to 16). At this visit the first dose of study medication will be applied under the supervision and management of the trial personnel (the subsequent doses will be applied at home).

Subjects, who are completely cleared in the selected treatment area (an AK count of zero), will continue in the Follow-up Period until trial completion at Month 36 (Visits 11 to 14).

Visit 7 – Only if Retreatment is required (3 days after Visit 6 with a visit window of +2 days)

Visit 7 will include:

- Clinical assessment of neoplasia in the selected treatment area (biopsy if there is suspicion of SCC, BCC or other neoplasia)
- Dermatologic examination of the selected treatment area(s) including LSRs
- Reporting of (S)AEs (see [Table 2](#))
- Reporting of concomitant medication, treatments and procedures
- Return of trial medication (for subjects treated with ingenol mebutate)
- Trial medication compliance

Visit 8 – Only if Retreatment is required (Week 10, 14 days ± 2 days after Visit 6)

Visit will include:

- Clinical assessment of neoplasia in the selected treatment area (biopsy if there is suspicion of SCC, BCC or other neoplasia)
- Dermatologic examination of the selected treatment area(s) including LSRs

- 
- Reporting of (S)AEs (see [Table 2](#))
  - Reporting of concomitant medication, treatments and procedures
  - Trial medication compliance (for subjects treated with imiquimod)

Visit 9 – Only if Retreatment is required (Week 12, 28 days  $\pm$  3 days after Visit 6)

Visit 9 will include:

- Clinical assessment of neoplasia in the selected treatment area (biopsy if there is suspicion of SCC, BCC or other neoplasia)
- Dermatologic examination of the selected treatment area(s) including LSRs
- Reporting of (S)AEs (see [Table 2](#))
- Reporting of concomitant medication, treatments and procedures
- Return of trial medication and trial medication compliance (for subjects treated with imiquimod)

Visit 10 – Only if Retreatment is required (Week 16, 56 days  $\pm$  3 days after Visit 6)

Visit 10 will include:

- Clinical assessment of neoplasia in the selected treatment area (biopsy if there is suspicion of SCC, BCC or other neoplasia)
- Dermatologic examination of selected treatment area including LSRs and AK count

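### The only pregnancy test scheduled before the first dose is 14 to 42 days old at dosing; a test at Visit 2 would narrow this gap at little cost

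*Protocol*

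**What the plan says.** Criterion 4b in protocol 10.4.1 accepts women of "Childbearing potential, provided there is a confirmed negative urine pregnancy test prior to trial treatment, to rule out pregnancy". Section 10.6.6.3 repeats the requirement. Neither says how recent the test must be.

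The timing comes from the schedules in 3.1.1 and 10.7.1, which mark the urine test at Visits 1, 6 and 10. The visit descriptions in 10.1.3 agree:

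- **Screening (Visit 1, 14 to 42 days before Day 1):** "Female subjects of childbearing potential will have a urine pregnancy test".
- **Visit 2 (Day 1):** the criteria are checked again, then "Once eligibility is confirmed, assessment of the selected treatment area, including LSRs and AK lesion count will be performed". Randomisation and the supervised first dose follow. No pregnancy test is listed.
- **Visit 6 (Week 8):** the list includes "Urine pregnancy test for female subjects of childbearing potential". Women who have not cleared take the first dose of cycle 2 at this visit. Item 1 of 10.6.5.3 requires evaluations to be finished before medication is dispensed in each cycle.
- **Visit 10 (Week 16):** a further test, after all protocol dosing.

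Criterion 5 adds that women of childbearing potential "must be willing to use highly effective methods of contraception (Pearl index < 1%) at study entry until Week 20". Hormonal methods must have been in use "for at least one menstrual cycle prior to enrolment". No lead-in is stated for an intrauterine device or double barrier.

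**The concern.** The stated purpose of the test is to rule out pregnancy, yet at the visit where every randomised woman is first dosed the most recent result is at least two weeks old and may be six weeks old. The Visit 2 eligibility check names no new test, so it relies on that result. The plan does better in cycle 2, where test and dose share a visit. It also tests cleared women at Visit 6 who receive no second cycle.

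Two routes to an undetected pregnancy remain:

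- a conception too recent to show at screening, in a woman newly starting a method that needs no lead-in;
- contraceptive failure between screening and Day 1.

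Either way, unless pregnancy is suspected sooner, she could complete cycle 1 (3 ingenol mebutate or 12 imiquimod doses) before the next scheduled test. If she is identified after randomisation she stays in the full analysis set (10.10.1) and, if withdrawn, is not replaced (10.5).

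**Working it through.** **Intervals from the documents**

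- The plan's own figure is the Visit 1 window, −42 to −14 days. Test age at first dose is therefore 14 to 42 days in cycle 1. In cycle 2 it is 0 days.
- Visit 6 is Day 57 ± 3, that is Day 54 to 60. Subtracting Day 1, the next scheduled test is 53 to 59 days after the first dose.

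**Assumptions (the documents give none of these)**

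- 5 to 50 women of childbearing potential, roughly 1% to 10% of 480.
- 1 to 25 of them newly starting a method without a lead-in.
- A window *w* of 7 to 21 days after conception in which a urine test is negative.
- 1 to 10 conceptions per 100 woman-years before entry.
- 1 per 100 woman-years after screening. Criterion 5 asks for a Pearl index below 1, so this is the ceiling if contraception performs as required.

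Let *g* be the gap in days between the Visit 1 test and the first dose.

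**Route 1: conceived before screening, too early to detect**

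Risk per woman = *w*/365.25 × rate.

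- Minimum: 7/365.25 × 1% = 0.019%.
- Maximum: 21/365.25 × 10% = 0.575%.

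Share a Visit 2 test would find = min(*g*, *w*)/*w*.

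| Women | Risk each | Expected | Found, *g* = 14 | Found, *g* = 42 |
|---|---|---|---|---|
| 1 | 0.019% (*w* = 7) | 0.0002 | 0.0002 | 0.0002 |
| 25 | 0.575% (*w* = 21) | 0.144 | 0.144 × 14/21 = 0.096 | 0.144 |
| 50 (upper bound) | 0.575% (*w* = 21) | 0.287 | 0.287 × 14/21 = 0.192 | 0.287 |

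The last row treats every woman as a new starter and ignores established methods.

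**Route 2: conceived between screening and Day 1**

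Risk per woman = *g*/365.25 × 1%, which is 0.038% at 14 days and 0.115% at 42 days. Share found = max(0, *g* − *w*)/*g*.

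- Minimum: 5 × 0.038% = 0.002 expected.
- Maximum: 50 × 0.115% = 0.057 expected.
- *g* = 14: none found if *w* = 21; half found if *w* = 7.
- *g* = 42, *w* = 21: half found, 0.057 × 0.5 = 0.029.
- *g* = 42, *w* = 7: 35/42 = 0.833 found, 0.057 × 0.833 = 0.048.

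**The case against.** The strongest reply is that nothing is broken and almost nothing is at risk. Criterion 4b asks for a negative test before treatment and the schedule supplies one; no section sets a maximum age. The expected counts rest on assumed inputs, span nearly three orders of magnitude for the first route, and stay below one pregnancy even at the extremes.

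Documented harm is limited. The imiquimod SmPC (Appendix V) has no clinical data on exposed pregnancies and advises caution. It also reports no harm in animal studies, no quantifiable serum levels and absorption below 0.9%, and does not list pregnancy as a contraindication. The ingenol mebutate SmPC is not reproduced, so no hazard can be argued for that arm.

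There are other safeguards: the Visit 2 eligibility recheck, contraception to Week 20, contacts at Day 4, Week 2 and Week 4 at which imiquimod could still be stopped, unscheduled visits for suspected pregnancy, and mandatory pregnancy follow-up. National requirements (10.4) might add a test, but those documents are not available here. After approval, rewording an inclusion criterion would also need the amendment process in 10.14.

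All of this stands, and it keeps the point minor. It does not justify testing at Visit 6 in women who will not be dosed again while omitting the test at the one visit where all are dosed. A recheck without a test cannot reveal a pregnancy that the woman does not suspect.

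**Conclusion.** The point holds as an optional, low-cost safety improvement. The intervals are firm: the last test is 14 to 42 days old at the first dose, against same-visit testing in cycle 2, and the next one comes 53 to 59 days after the first dose. There is no contradiction in the protocol, no eligibility deviation, and no effect on the SCC endpoint.

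The number of women affected is uncertain but small. Under the stated assumptions, 0.0002 to 0.14 conceptions too early for the screening test are expected among new starters (0.29 if all 50 women are counted), and 0.002 to 0.06 between screening and Day 1. A Visit 2 test would find much of the first group and, depending on the gap and the detection window, from none to most of the second. The counts make no allowance for women not using their method as required after screening, which the documents do not quantify.

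**What to change.** Mark the urine pregnancy test at Visit 2 in the tables of 3.1.1 and 10.7.1. In the Visit 2 text of 10.1.3, state that it is done before randomisation and first dosing, so that a positive result is a screening failure and not a randomised subject. Put the same timing into criterion 4b and 10.6.6.3, for example: negative urine pregnancy test at Visit 2, before randomisation.

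- **Preferred:** keep the Visit 1 test and repeat it at Visit 2. This preserves the check before the screening biopsy and costs one dipstick per woman of childbearing potential (5 to 50 under the assumption above). Sites already run the test at three visits.
- **Alternative:** move the Visit 1 test to Visit 2. This adds no test, but an occasional pregnancy would be found only after a biopsy under anaesthetic with a vasoconstrictor (10.7.4.1).

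Otherwise the cost is wording in two tables, one visit description, one criterion and one precautions paragraph. If the protocol is already approved, the change is best carried with another amendment. A very recent conception would still be missed.

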#### 10.4.2 Exclusion Criteria

1. Location of the selected treatment area:
  - on the periorbital skin
  - on the perioral skin/around the nostrils
  - within 5 cm of an incompletely healed wound
  - within 10 cm of a suspected BCC or SCC or other neoplasia
2. Selected treatment area lesions that have atypical clinical appearance (e.g., hypertrophic, hyperkeratotic or cutaneous horn).
3. History of SCC, BCC, malignant melanoma or other neoplasia in the selected treatment area.
4. History or evidence of skin conditions other than the trial indication that would interfere with evaluation of the trial medication in the selected treatment area (e.g., eczema, unstable psoriasis, xeroderma pigmentosum).
5. Use of ingenol mebutate and/or imiquimod in and within 5 cm of the selected treatment area within 2 years prior to Screening (Visit 1).
6. Use of cosmetic or therapeutic products and procedures which could interfere with the assessments of the treatment area.
7. Anticipated need for hospitalisation or out-patient surgery prior to Day 15 in the initial treatment cycle. Note that cosmetic/therapeutic procedures are not excluded if they fall outside of the criteria detailed in Prohibited Therapies or Medications (see Exclusion Criteria Nos. 18- 19).
8. Known sensitivity or allergy to any of the ingredients in ingenol mebutate gel or imiquimod cream.
9. Organ transplant recipients
10. Immunosuppressed subjects (for example HIV patients)
11. Clinical diagnosis/history or evidence of any medical condition that would expose a subject to an undue risk of a significant AE or interfere with assessments of safety and efficacy during the course of the trial, as determined by the investigator's clinical judgment
12. Presence of acute sunburn within the selected treatment area
13. Current enrolment or participation in a clinical trial within 30 days of entry into this trial.

- 
14. Subjects previously randomised in the trial.
  15. Female subjects who are breastfeeding.
  16. Subjects who are institutionalised by court order or by the local authority
  17. In the opinion of the investigator, the subject is unlikely to comply with the Clinical Study Protocol (e.g. alcoholism, drug dependency or psychotic state)

**Prohibited Therapies and/or Medications: within 4 weeks prior to Screening (Visit 1):**

18. Treatment with immunomodulators (e.g., azathioprine), cytotoxic drugs (e.g., cyclophosphamide, vinblastine, chlorambucil, methotrexate, podophyllin, camptothecin) or interferon /interferon inducers.
19. Treatment with systemic medications that suppress the immune system (e.g., cyclosporine, prednisone, methotrexate).

#### **10.4.3 Subject Screening Log**

A subject screening (enrolment) log will be maintained by the site during the trial. All subjects who sign the informed consent will be included on the screening log and in the CRF.

#### **10.4.4 Subject Registration**

At Visit 1, each subject will be assigned the next (ascending) CRF book number available at the trial site. The CRF book number is a unique subject identifier used throughout the trial, in lieu of the subject's name.

It is completely distinct from the trial medication kit number(s) assigned to the subject.

### **10.5 WITHDRAWAL CRITERIA**

The investigator is free to withdraw the subject at any time for medical reasons.

Subjects **may** withdraw for any of the following reasons:

1. *Unacceptable adverse events or LSRs*: any adverse event or LSR that the investigator or the subject considers unacceptable.
2. *Exclusion criteria*: any exclusion criteria which emerge/become apparent during the subject's participation in the clinical trial.
3. *Voluntary withdrawal*: subjects will be free to withdraw from the clinical trial at any time and for any reason.
4. *Other reasons*: other reasons than stated above which requires the subject to (be) withdraw(n) should be specified.

Subjects, who are discovered, after randomisation, not to have fulfilled all in-/exclusion criteria at time of enrolment, should be withdrawn from treatment unless the investigator, based on clinical and ethical evaluation, finds withdrawal from treatment inappropriate. If a biopsy is taken for suspicion of neoplasia in the treatment area, the subject should likewise be withdrawn from treatment.

Such deviation(s) from the (Consolidated) Clinical Study Protocol must be reported to LEO Pharma A/S (and the IEC/IRB, as appropriate) and recorded in the Clinical Study Report.

Subjects who withdraw from the trial should be asked to complete the early termination visit.

Reason(s) for withdrawal will be recorded in the CRF.

Subjects withdrawn after randomisation will not be substituted.

## 10.6 INVESTIGATIONAL PRODUCTS

### 10.6.1 Ingenol Mebutate

Finished product (brand) name (if available)/name investigational product	Ingenol mebutate gel, 0.015% / Picato ®
Formulation	Gel
Active ingredient name/concentration	Ingenol mebutate 0.015% w/w
Excipients	Isopropyl alcohol Ph. Eur. Hydroxyethyl cellulose Ph. Eur. Benzyl alcohol Ph. Eur. Citric acid monohydrate Ph. Eur. Sodium citrate dihydrate Ph. Eur. Purified water Ph. Eur.
Pack size(s)	0.47 g
Manufacturer's name of bulk medication (IP)	LEO Laboratories Ltd, Ireland or DPT Laboratories Ltd., US
Certifier's name of bulk medication (IP)	LEO Pharma A/S
Supplier's name	Almac Clinical Services

Manufacturer's name of subject treatment packages	Almac Clinical Services
Certifier's name of subject treatment packages	LEO Pharma A/S

